There is a small risk that participants may disclose examples of serious unsafe practice that have not yet been reported through the usual procedures. Any information given by participants throughout the study indicating harm to patients or professional misconduct may be disclosed by the research team as part of a safeguarding process, in accordance with established good research practice and with the University of Manchester's own policy on whistleblowing and public interest disclosure. Of course, our participant information sheet and consent form will explicitly mention this issue. If this situation occurs, the interview will be stopped and the matter discussed with the participant making it clear what is happening, before discharging that responsibility. In the unlikely event of uncovering a previously unreported serious adverse event that directly resulted in patient harm, the researcher might be professionally obliged to report the incident through the normal risk management procedures. The terms on these issues will be clearly stated on the participant information sheet.

Statement of indemnity

The University has insurance available in respect of research involving human subjects that provides cover for legal liabilities arising from its actions or those of its staff or supervised students. The University also has insurance available that provides compensation for non-negligent harm to research subjects occasioned in circumstances that are under the control of the University.

Success criteria, potential barriers/risks to the research and risk mitigation

The main success criteria for this project are, straightforwardly, the delivery to time and target of the five main workpackages described above and the planned outputs already outlined. In the table below we set out our analysis of the potential risks to delivery of each workpackage and our approach to minimising and mitigating those risks.

ID	Risk description	WPs affected	Likeli- hood	Impact	Description of impact	Mitigating actions
1	Access to Hospital Episode Statistics /PHIN delayed	WP1 WP4 WP5	Low	Medium	Delay to quants analysis in WP1/4 and impact on case study work in WP3	Work on applications for data access to start as soon as funding approval and in advance of formal project start date. PHIN CMO is co-app, NHSD have expressed support and team have extensive experience of applications
2.	Access to ADAPt data delayed or not possible	WP5	Low	Medium	Delay or non- completion of quants analysis in WP5	Unlikely as ADAPt is central to deliver government commitment to Paterson inquiry recommendation 1 and pilots complete by March 2022. Team could seek CAG approvals to link Hospital

						Episode Statistics and PHIN data using patient identifiable data ourselves without ADAPt.
3	Data security breach	WP1 WP4 WP5	Low	High	Data access revoked.	UoM and UoY have strict data security protocols accepted by providers such as CPRD and NHS Digital. PHIN data could be analysed on PHIN servers eg without leaving PHIN secure environment.
4	Poor uptake of survey	WP2	Medium	Medium	Issues of generalisability and value of survey findings	Pre-survey engagement, strong support from PAG stakeholders and encouragement to complete,
5	Poor engagement with case studies	WP3	Medium	Medium	Difficulty undertaking or completing fieldwork	Careful case study selection and pre- engagement work, support from CQC/IPHN, good incentives to participate because of bespoke quants resources.
6	Research team changes or sickness/ absence	All	Low	Medium	Difficulties completing workpackages to time and target	Early start to recruitment of research fellow and administrator. Strong support from UoM HR and research office.

Acknowledgement and disclaimer

This study/project is funded by the NIHR [HSDR NIHR135108]. The views expressed are those of the author(s) and not necessarily those of the NIHR or the Department of Health and Social Care.

References

References

1 Institute for Fiscal Studies. Recent trends in independent sector provision of NHS-funded elective hospital care in England. London: IFS, 2019. https://ifs.org.uk/publications/14593

2 https://www.england.nhs.uk/2020/03/nhs-strikes-major-deal-to-expand-hospital-capacity-to-battle-coronavirus/

3 James G. Report of the Independent Inquiry into the Issues raised by Paterson. London: HMSO, 2020. https://assets.publishing.service.gov.uk/government/uploads/system/uploads/attachment_data/file/86321 https://assets.publishing.service.gov.uk/government/uploads/system/uploads/attachment_data/file/86321 https://assets.publishing.service.gov.uk/government/uploads/system/uploads/attachment_data/file/86321 https://assets.publishing.service.gov.uk/government/uploads/system/uploads/attachment_data/file/86321 https://assets.publishing.service.gov.

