For WP2, data on volume will be linked to responses to our national survey of governance leads in NHS and independent hospitals. For WP3 we will provide information on potential clusters of NHS and independent hospitals to inform case study selection. For WP4 and WP5 we will provide information on volume, case-mix and coding practice for areas of overlap across the NHS and independent sector. This list is likely to include procedures in specialties such as general surgery, urology, trauma and orthopaedics, ENT, ophthalmology and cardiology.

Case-mix

Using patient level data from Hospital Episode Statistics we will compare the case-mix of patients. This will include patients whose treatment is NHS funded regardless of where the treatment occurs, and privately funded care in NHS private patient units. We will compare patient socio-demographic characteristics (gender, age, ethnicity, deprivation of the patient's local area) and medical characteristics (length of stay, presence and count of comorbidities). These case-mix variables will be summarised by provider type (NHS hospital, NHS private patient unit), funding source, geographical region and over time.

For our analysis of case-mix we will estimate a prediction model for patients in quadrants A, B and C using mortality as the outcome for each patient. We will compare expected vs actual outcomes for patients in each quadrant after performing adjustment for casemix variables and provider characteristics. We will summarise the mean risk ratios for patients in each quadrant to identify

differences that may arise due to differences in casemix. We will repeat the analyses for the clinical specialties with the highest volumes across the three quadrants. Findings from this analysis will inform WP4 and WP5.

Coding practice

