We have some information about the clinical governance arrangements in the NHS and independent sector [7, 9] but we know little about how those governance processes work in practice and are experienced, particularly at the interface between organisations/hospitals. As noted earlier a number of reports have made recommendations concerning the way NHS and independent hospitals should work collaboratively to improve clinical governance but we do not know whether or how those recommendations have been taken up and enacted in practice.

We plan to undertake a survey of individuals involved in leading clinical governance in NHS and independent hospitals. After consultations with our stakeholders noted earlier, we think there is value in securing a range of different perspectives at an organisational level if we are to really understand how clinical governance works in practice. For that reason, and with the support of NHS England and the Care Quality Commission we will survey medical directors, director of nursing/chief nurses and clinical governance leads at all 169 acute NHS trusts; and with the support of IHPN we

will survey hospital directors, matrons and chairs of Medical Advisory Committees at 342 independent hospitals providing inpatient care.

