We will undertake extensive pre-survey development and engagement work where we will consult with stakeholders to develop a survey that captures data that is meaningful, relevant and useful to respondents. During this time we will also develop our sampling frame of contacts from NHS and independent hospitals to identify individuals who are best placed to complete the survey. We carried out similar pre-engagement work with stakeholders for our current NIHR funded project about locum doctors and a previous NIHR-funded project on medical revalidation. In both cases we engaged with stakeholders, such as, medical directors and responsible officer networks to develop our survey and identify potential respondents. In our experience, this helps not only to develop a survey that will be of interest and use to respondents but also helps respondents understand why we are doing the survey and be supportive of its completion. Our piloting work will also include cognitive interviewing to uncover whether the questions work as intended, and whether the survey takes sufficient account of differences in organisational context/setting and respondents' roles, knowledge and expertise. Our national survey of responsible officers in both NHS and independent healthcare providers secured a response rate of 63% [32] and our current survey of medical directors about locum doctors has an interim response rate of 48% to date. We will offer to provide all respondents with the results of the survey so they can see how their own experiences relate to those of others, and we find this also helps to secure engagement.

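### The WP1–WP2 link is described for survey responses; attaching volume to all 511 surveyed organisations would let non-response be examined at little cost

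*Protocol*

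**What the plan says.** **The link.** The Protocol's WP1 Volume section explains how WP1 feeds the other work packages. For WP2 it says that "data on volume will be linked to responses to our national survey of governance leads" in NHS and independent hospitals.

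**The frame.** WP2 approaches everyone on a known list: "medical directors, director of nursing/chief nurses and clinical governance leads at all 169 acute NHS trusts", and for the independent sector the team "will survey hospital directors, matrons and chairs of Medical Advisory Committees at 342 independent hospitals providing inpatient care". The unit approached is the person: "We plan to undertake a survey of individuals involved in leading clinical governance in NHS and independent hospitals".

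**Response.** The WP2 section gives two precedents: "Our national survey of responsible officers in both NHS and independent healthcare providers secured a response rate of 63" per cent, and "our current survey of medical directors about locum doctors has an interim response rate of 48% to date". It states no target or expected rate for WP2 itself.

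**The risk.** Risk 4 in the table under Success criteria rates poor survey uptake medium for both likelihood and impact, and describes the impact as "Issues of generalisability and value of survey findings". The mitigations listed all aim at raising response.

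**The volume data.** Under Patient datasets, HES covers NHS-provided and NHS-funded care, and all providers are under an order to submit privately funded admitted care to PHIN. WP1 combines the two sources so that all four funding and provision quadrants are covered.

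**The concern.** A link built on responses attaches nothing to organisations that stay silent. Volume is one of the few characteristics that WP1 should be able to derive for responders and non-responders alike, so it is a natural variable for judging who is missing.

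If larger organisations both reply more often and have more developed shared governance, unweighted percentages would overstate how common such arrangements are. That would affect the WP2 contribution to RQ2, on how well organisations understand and oversee scope of practice. The respondent data planned in WP2 (role, workplace, demographics) describe those who reply; without frame data they cannot show how the others differ.

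**Working it through.** **1. Inputs from the Protocol.** Frame: 169 + 342 = 511 organisations. Three roles are named in each sector, so about 3 × 511 = 1,533 invitations if there is one person per role. Precedent response: 63%, and 48% interim.

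**2. Precedent non-response.** 1 − 0.63 = 0.37 and 1 − 0.48 = 0.52. Both rates are for persons, and they come from other surveys.

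**3. From persons to organisations.** With three invitees, the share of organisations with no reply depends on how alike colleagues behave (correlation rho, beta-binomial model; rho is assumed).

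| rho | at 37% person non-response | at 52% person non-response |
|---|---|---|
| 0 | 0.37³ = 5% (26 of 511) | 0.52³ = 14% (72) |
| 0.3 | 14% (70) | 26% (131) |
| 1 | 37% (189) | 52% (266) |

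So 37% to 52% of organisations being silent is the extreme case in which all three colleagues always act alike.

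**4. Illustrative bias, respondent level.** Assumed, not from the Protocol: two equal volume groups, and a given arrangement reported by 70% in the high-volume group and 40% in the low-volume group, so the true value is 55%. The unweighted estimate is (r_h × p_h + r_l × p_l) / (r_h + r_l).

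- Response 63% v 48%: (0.63 × 0.70 + 0.48 × 0.40) / 1.11 = 0.633 / 1.11 = 57.0%, bias 2.0 points.
- Response 70% v 40%: (0.70 × 0.70 + 0.40 × 0.40) / 1.10 = 0.650 / 1.10 = 59.1%, bias 4.1 points.

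Inviting three people per organisation does not change this, because all three share the same volume group. (63% and 48% are used here as an assumed gap between volume groups; the Protocol does not present them that way.)

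**5. Illustrative bias, organisation level.** Suppose any one of three independent replies counts. Then an organisation is represented with probability 1 − (1 − r)³.

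- 63% v 48% becomes 94.9% v 85.9%: (0.949 × 0.70 + 0.859 × 0.40) / 1.809 = 55.7%, bias 0.7 points.
- 70% v 40% becomes 97.3% v 78.4%: (0.973 × 0.70 + 0.784 × 0.40) / 1.757 = 56.6%, bias 1.6 points.

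Correlation between colleagues would move these towards the figures in step 4.

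**6. Cost of weighting.** With equal groups and weights 1/r, the Kish design effect is (r_h + r_l)(1/r_h + 1/r_l) / 4.

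- 63% v 48%: 1.11 × 3.671 / 4 = 1.02.
- 70% v 40%: 1.10 × 3.929 / 4 = 1.08.

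In these scenarios weighting recovers 55% exactly, but only because volume is made the sole cause of the bias.

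**The case against.** The strongest reply is that nothing in the Protocol is wrong. The linkage sentence sits in a paragraph on how WP1 feeds the other packages and does not exclude a wider link. Comparing responders with non-responders and weighting are ordinary analysis-plan content, and no such plan is at hand. A reader might infer that volume will be linked to responses alone and that non-response will go uncorrected; the text supports neither statement.

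Three other inferences also go too far.

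- 37% to 52% is not an expected non-response rate for WP2. It comes from two other surveys, one of them still open, and describes persons rather than organisations.
- The data are not yet in hand. Access is still to be agreed, and PHIN data are aggregated and stay in PHIN's own environment. HES alone omits independent hospitals' privately funded work, so volume groups built on HES alone could misplace some of them.
- The risk table's mitigation entry ends on a comma, so the list may be incomplete. WP2 also describes substantial work to raise response.

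All of this stands, as do two limits on the benefit. No passage says that volume predicts response or governance. And organisation volume cannot explain why one role replied and a colleague did not. WP2 also seeks experiences and a range of initiatives, not only percentages.

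What remains is narrower. The Protocol itself sets the scope of the link, describes it for responses, and names generalisability as a risk, while no passage describes using the planned volume data to examine that risk.

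**Conclusion.** The point holds as a cheap improvement, not as an error or contradiction. The frame is known, the volume sources do not depend on reply, and the planned link to responses already implies that volume can be matched to surveyed organisations.

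The likely gain is modest and rests on assumed inputs: about 2.0 to 4.1 points of bias for respondent-level percentages, and about 0.7 to 1.6 points at organisation level when any of three independent replies counts. If volume is unrelated to response or to governance, the gain in bias is nil, but the comparison would still give evidence on representativeness that the Protocol does not otherwise plan.

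**What to change.** Amend the WP2 linkage sentence in the WP1 Volume section so that volume, sector and region are attached to the full frame of 511 organisations, using HES plus PHIN outputs as far as the access terms allow. Then:

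- compare responding with non-responding organisations on these variables;
- report results weighted by the inverse of the response rate in sector-by-volume cells, as a sensitivity analysis beside the unweighted results;
- state that this corrects only the non-response that these variables explain.

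Settle this before data requests and survey identifiers are fixed, so that the match is possible. The cost is one changed sentence, a small extra analysis, and slightly wider intervals for the weighted results (design effect about 1.02 to 1.08 in the scenarios above).

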We will organise the project into five main work packages, which are listed below (with the principal research questions they link to in brackets) and are then described in detail:

- WP1 Variations in hospital volume, case-mix and coding practice (RQs 1, 4)
- WP2 National survey of clinical governance leads in NHS and independent hospitals in England (RQs 2, 4)
- WP3 In depth case studies of clinical governance in a number of linked pairs or clusters of NHS and independent hospitals (RQs 2, 4)
- WP4 Analysis of the scale and scope of consultant clinical practice (RQs 2, 3, 4)
- WP5 Analysis of the quality and safety of care (RQs 3, 4)

Sample size summary

In WP1, WP4 and WP5 hospital admitted patient care will be used. The data used cover the majority of the English population and the sample size will be very large.

In WP 2, we will survey medical directors, director of nursing/chief nurses and clinical governance leads at all 169 acute NHS trusts; and with the support of IHPN we will survey hospital directors, matrons and chairs of Medical Advisory Committees at 342 independent hospitals providing inpatient care.

In WP3, we anticipate interviewing approximately eighty staff across all four case study sites.

In WP5, we aim to recruit around forty patients and carers to take part in around six focus groups. If patients or carers prefer, we can conduct one-to-one interviews.

Patient datasets

The quantitative analyses for this project will use four main patient-level datasets provided by NHS Digital and PHIN. We set out here a brief description of each dataset and our rationale for its use in the research. Details of our methods and analytic approach are given in the workpackage descriptions.

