For each index admission we will calculate a set of quality and safety indicators, which have been validated for use with administrative data and are widely used for performance assessment in regulatory contexts (for example in monitoring against the NHS Outcome Framework, in CQC inspections/reviews, in clinical governance and appraisal/revalidation processes, etc) and for research purposes:

- 1) Unplanned readmission to hospital within 28 days of discharge (binary: yes/no),
- 2) Unplanned emergency department attendance within 28 days of discharge (binary: yes/no),
- 3) Emergency transfers to NHS hospitals at the end of the index admission episode (binary: ves/no).
- 4) Total length of continuous inpatient stay (accounting for transfers between hospitals) (continuous).
- 5) Death within 30 days of admission (binary: yes/no), and
- 6) Patient-reported health improvements within the first 6 months after surgery (for hip and knee replacement only) (continuous).

Each indicator will be summarised for index admission for quadrants A, B and C. Indicators 1-4 are constructed by linking index admissions to subsequent episodes of hospital care within Hospital Episode Statistics, which allows for such longitudinal follow-up through the use of a unique pseudonymised patient identifier (the Master Person Service ID). For indicator 2, we will additionally link admitted patient data to the Hospital Episode Statistics Emergency Care dataset, which captures all emergency department attendances in English hospitals from 2021.

Indicator 5 is constructed by linking Hospital Episode Statistics data to official Civil Registration data on date of death held by the Office for National Statistics. This linkage is performed by NHS Digital

based on the patient-identifiable data (e.g name, date of birth, NHS number) they hold. We will also consider an alternative outcome indicator based on in-hospital deaths as recorded in Hospital Episode Statistics (derived from the data fields discharge method & destination). This alternative approach captures mortality for the full patient population, including those that do not have an NHS number (e.g. patients not resident in England) or that for other reasons cannot be linked to Civil Registration data, but it necessarily fails to capture any deaths that occur after the end of the index hospital admission.

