Indicator 6 uses patient-reported outcome measures (PROMs) data that are routinely collected in both NHS and independent hospitals for two surgical procedures: planned hip and knee replacement surgery (see section on datasets above). We will request NHS Digital to supply us with data from the national PROMs programme, which covers NHS-funded care only, linked to a corresponding Hospital Episode Statistics extract.

We will conduct separate multivariate regression analysis of the six indicators stratified by type of procedure. All regression models will include a set of indicator variables denoting the three quadrants, and the associated regression coefficients will be used to test for differences in quality and safety across hospital types and funding sources. All regression models will control for known confounders such as patient demographic characteristics (i.e. sex, age, ethnicity, area-level deprivation based on the index of multiple deprivation score for the patient's lower-layer super output area (LSOA) of residence), diagnosis, comorbidities, past healthcare utilisation as captured in Hospital Episode Statistics, and admission information (e.g. calendar month of admission). In specifying the case-mix adjustment we will draw on previous work [40, 41, 42] and insights from the data quality assessment conducted in WP1.

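### WP1 classes length of stay as a case-mix variable and adjusts its mortality model for case-mix variables, so as written the model conditions on a result of care

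*Protocol*

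**What the plan says.** The Case-mix part of WP1 sets out socio-demographic characteristics and then "medical characteristics (length of stay, presence and count of comorbidities). These case-mix variables will be summarised by provider type", funding source, region and time. Length of stay thus sits beside comorbidity in a list that the protocol itself names as the case-mix variables.

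The next paragraph turns from description to modelling: "we will estimate a prediction model for patients in quadrants A, B and C using mortality as the outcome for each patient". Expected and actual outcomes are compared in each quadrant "after performing adjustment for casemix variables and provider characteristics". Mean risk ratios per quadrant are then meant to show "differences that may arise due to differences in casemix". The paragraph ends: "Findings from this analysis will inform WP4 and WP5".

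WP5, in its list of quality and safety indicators, makes the same quantity an outcome. Indicator 4 is "Total length of continuous inpatient stay (accounting for transfers between hospitals". The WP5 regressions have their own adjustment set: patient demographics followed by "diagnosis, comorbidities, past healthcare utilisation as captured in Hospital Episode Statistics, and admission information (e.g. calendar month of admission". Length of stay is not named there.

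**The concern.** A case-mix adjustment should describe what patients bring to the admission. Length of stay does not qualify. It is complete only when the patient is discharged, transferred or dies. Complications lengthen it, in-hospital death cuts it short, and local discharge practice shifts it at unchanged patient risk.

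Transfers add a difficulty tied to quadrant. WP5 indicator 3 is emergency transfer to an NHS hospital at the end of the index episode, and indicator 4 is defined to account for transfers. The WP1 list carries no such qualification. If stay in WP1 were measured at the first provider only, a deteriorating patient moved out of an independent hospital would be recorded with a short stay, for a reason linked to both quadrant and death.

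At stake is the meaning of the WP1 risk ratios. With length of stay in the model, differences in care or discharge practice are absorbed into expected deaths and read as patient mix, which is what the analysis is meant to separate out.

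**Working it through.** **Reading the text.**

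1. The protocol defines case-mix variables for WP1 once, and length of stay is in that list.
2. The mortality model adjusts for case-mix variables, using the same term one paragraph later and excepting nothing.
3. The natural reading is therefore that length of stay is a covariate in the expected-mortality model.
4. WP5 treats length of stay as a result of care and adjusts for factors known at or before admission.

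WP1 and WP5 thus give the same quantity two incompatible roles.

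**Size.** The protocol states no event rate, risk ratio or difference in stay between quadrants for this analysis. It says only that "The data used cover the majority of the English population and the sample size will be very large". There is no figure to reproduce. A large sample reduces random error but not this bias.

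**Illustration (every input is an assumption).** 1.5 million admissions, 5% in quadrant C and the rest in A. Pre-admission risk x is standard normal, with the same distribution in both quadrants. With q = 1 for C and c = 1 for a complication:

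- logit P(complication) = −3 + 0.7x + log(OR)·q
- stay = Gamma(shape 2, scale 1) × exp(0.2x + 1.2c + log(m)·q), where m is the multiplier for discharge practice in C
- logit P(death) = −6.5 + 0.7x + 2.5c

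A logistic mortality model without a quadrant term gives expected deaths. For each quadrant, O/E = observed deaths ÷ sum of predicted probabilities. The result is O/E in C divided by O/E in A, once with x alone and once with x and log stay.

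| Complication OR in C | Stay multiplier in C | C:A without stay | C:A with stay | With ÷ without |
|---|---|---|---|---|
| 1 | 1 | 1.01 | 1.01 | 1.00 |
| 1 | 0.8 | 0.97 | 1.14 | 1.18 |
| 1 | 0.6 | 0.99 | 1.42 | 1.43 |
| 1 | 1.25 | 0.97 | 0.83 | 0.86 |
| 1.5 | 1 | 1.18 | 1.13 | 0.96 |
| 2 | 1 | 1.45 | 1.31 | 0.90 |
| 0.5 | 1 | 0.81 | 0.86 | 1.06 |
| 2 | 0.8 | 1.35 | 1.47 | 1.09 |

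Monte Carlo error is roughly 5–6% per ratio. That is why two rows with the same complication OR of 2 show 1.45 and 1.35 without stay. Within a row both models use the same simulated deaths, so observed deaths cancel from the last column, which reflects only the change in expected deaths.

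**What it shows.**

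- Row 1: no distortion when care and discharge practice are the same.
- Rows 2–4: equal mortality, but a difference appears, upward if C discharges earlier and downward if later.
- Rows 5–7: a true difference in care is pulled towards 1.
- Row 8: the two mechanisms together can exaggerate a true difference.

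The simulation leaves out truncation of stay by death and by transfer, so it does not cover every route to bias.

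**The case against.** The strongest case on the other side has four parts.

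- **The list is introduced for description, and the model's covariates are named by reference rather than itemised.** This is true, and summarising stay by quadrant is harmless. But the protocol does not merely leave the covariates open. It calls length of stay a case-mix variable and then adjusts for case-mix variables. An analysis plan that followed this wording would inherit the problem.
- **WP5 is unaffected.** A reader might infer from the statement that WP1 findings inform WP4 and WP5 that the flaw passes into the WP5 case-mix adjustment. The protocol does not support that. WP5 has its own adjustment set without length of stay. It draws on previous work and on the WP1 data quality assessment, which most naturally means the coding completeness and depth work. Informing later work packages with findings is not the same as copying a covariate set. Carry-over is a risk, not a fact.
- **WP1 is not the test of quality.** It serves RQ1 and RQ4. The comparison of quality and safety sits in WP5, with instrumental-variable models for unobserved confounding. This stands and limits the consequence. It does not rescue the WP1 analysis, whose own aim of isolating patient mix is undermined when a result of care is counted as patient mix.
- **The simulated sizes say nothing about this study.** This also stands. They show direction and mechanism only.

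**Conclusion.** The point holds for the WP1 expected-versus-actual mortality comparison. Followed as written, the protocol puts a variable determined after admission, and treated as an outcome in WP5, into the model for expected deaths. It is a stated rule that is wrong, not a missing detail.

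The conclusion rests on reading the case-mix term in the modelling paragraph as the list defined just before it. Bias arises if stay differs between quadrants through complications, transfers or discharge practice. It does not arise if stay differs only through risk present before admission. Its direction can go either way and its size cannot be derived from the protocol. The simulated shifts, factors of 0.86 to 1.43, hold only under the assumed inputs.

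Two stronger readings are not supported: that the WP1 comparison is certainly biased by a known amount, and that the WP5 quality comparison is itself biased.

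**What to change.** In the Case-mix part of WP1, take length of stay out of the adjustment set for the mortality model. State that this model uses only factors fixed at or before admission, in line with the WP5 set: age, sex, ethnicity, area deprivation, diagnosis and procedure, pre-existing comorbidities, and past healthcare use. Keep length of stay as a descriptive variable in WP1 and as an outcome in WP5. Add a sentence that any case-mix specification taken from WP1 into WP4 or WP5 excludes it.

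The cost is a few words of protocol text, settled before the models are run. The model loses one covariate, and the Hospital Episode Statistics data already planned are sufficient.
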